Trial participants will be invited to also consent for access to information from their annual clinic visits and HCV testing at any other contact with clinical services for up to 5 years, to detect re-infection.

*Illicit drug monitoring*

Illicit drug use will be recorded at baseline and at end of treatment (week 8 for genotype 3, week 12 for genotype 1). One sample of urine for toxicology will be taken during treatment. Those participants who fail to achieve SVR will be compared to successful participants for any correlation with particular substance use. For any candidate substance associated with failure to achieve SVR not explained by lack of adherence, biological samples will be analysed for biological mechanisms.

*Adherence monitoring*

Adherence of those participants randomised to DOT will be documented on a daily log. Those randomised to fortnightly collection of medication will receive Zepatier tablets in blister packaging. They will return their packets of medication every two weeks and any remaining tablets will be counted. Participants infected with HCV genotype 3 will additionally receive bottles containing Sovaldi tablets. These bottles will be fitted with adherence aid caps that record time and date of each cap opening.

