### **5.5.2 Treatment Allocation**

Eligible participants infected with genotype 1 HCV will receive Zepatier treatment for 12 weeks. Zepatier contains a combination of Grazoprevir and Elbasvir. Whilst it is a licensed medication, Merck will supply GMP ready investigational medical product (IMP) for use in the trial. Those infected with genotype 3 HCV will receive commercial stock sofosbuvir off the shelf in addition to Zepatier for 8 weeks. Treatment regimens for treatment naïve and treatment experienced participants enrolled in the trial will be the same. Zepatier tablets are film-coated and each contains 50 mg Elbasvir and 100 mg Grazoprevir. Sovaldi is provided as a single 400mg tablet.

For participants in group 1, medication will be dispensed daily by the participant's community pharmacist or at the needle exchange. The pharmacist or trial nurse will observe the participant taking the medication and this will be noted in a daily log. Participants will be provided with sufficient tablets for the weekend and other days that the pharmacy/needle exchange is closed. Participants in groups 2 and 3 will fortnightly receive two week's supply of medication from the trial staff. Participants infected with Genotype 1 HCV will be instructed to take one tablet daily from the blister pack. Those infected with Genotype 3 HCV will be instructed to take one tablet daily from the blister pack and one tablet daily from the bottle. The bottle will be fitted with an electronic adherence measuring aid.

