## **6 INVESTIGATIONAL MEDICINAL PRODUCT**

### **6.1 TRIAL DRUG**

#### **6.1.1 Trial Drug Identification**

Genotype 1 infection will be treated with Zepatier (100mg Grazoprevir and 50mg of Elbasvir) supplied as one film-coated tablet to be taken once per day with or without food for 12 weeks. This is a licensed medication but the drug supplied by the manufacturer will be IMP.

Genotype 3 infection will be treated with Zepatier as above plus Sovaldi (Sofosbuvir 400mg, licensed product), taken as one film-coated tablet once daily with food for 8 weeks. The combination of Zepatier plus Sovaldi has been successfully trialled for treatment of genotype 3 hepatitis C infection (C-SWIFT and C-ISLE trials) but this combination of drugs is not licensed for treatment of HCV genotype 3 infection.

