- c) Adherence: to compare the longitudinal evolution of adherence to the prescribed regimen between the conventional pathway and the pharmacy led pathway. For each patient, daily adherence will be defined using a binary variable  $Z_t$  indicating whether yes ( $=1$ ) or no ( $=0$ ) the subject has taken their medication on day  $t$ . This longitudinal binary variable will be directly generated from the patient electronically compiled dosing history. Comparison of binary time series is realized using a logistic regression where dependence among observations from a given patient over time is taken into account. The effect of pathway and contingency management on overall adherence will be tested using the above-described model by testing if either the group coefficient or the interaction between the group and time are significantly different from zero.
- d) Proportion who complete the course of those initiating treatment.

Multiple logistic regression modelling will explore the patient and pathway characteristics that are associated with the secondary outcomes and primary outcome. Patient outcomes considered will be age, gender, deprivation, employment, comorbidity, and the psycho-social variables assessed.

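### For genotype 3 in the fortnightly arms, the daily adherence variable records Sovaldi bottle openings and cannot show a missed Zepatier tablet

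*Protocol*

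**What the plan says.** Section 9.2.3(c) sets the aim of the adherence analysis as "to compare the longitudinal evolution of adherence to the prescribed regimen". Z_t equals 1 or 0 according to whether "the subject has taken their medication on day" t. The source is then fixed: "This longitudinal binary variable will be directly generated from the patient electronically compiled dosing history".

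Under section 5.5.2, genotype 3 participants collecting fortnightly are "instructed to take one tablet daily from the blister pack and one tablet daily from the bottle". The same section adds: "The bottle will be fitted with an electronic adherence measuring aid". Section 3.1 (Adherence monitoring) describes the device on the Sovaldi bottles: "These bottles will be fitted with adherence aid caps that record time and date of each cap opening". Section 6.1.4 likewise places the caps on the Sovaldi bottles, and Table 2 links cap-measured adherence to genotype 3 participants treated with Sovaldi.

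Zepatier comes in blister cards. Section 3.1 and Table 2 have leftover tablets counted at each two-week return. Section 9.2.2 names the daily log as the adherence source for DOT, and pill counts together with cap data for the fortnightly groups.

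**The concern.** The protocol states both what Z_t means and where its values come from, and for a two-drug regimen the second cannot deliver the first. The blister card leaves no electronic trace, so nothing in the electronic history can turn Z_t to 0 on a day when only Zepatier was missed. No section says how Zepatier intake enters Z_t.

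Two conclusions could be affected. The first is adherence by pathway. Adherence is a declared secondary outcome (section 6.4), and section 1.2 makes the case for fortnightly collection depend on adherence holding up without daily observation. In DOT the log records the medication as a whole on observed days; in the fortnightly arms one of the two genotype 3 drugs would be invisible to Z_t. The second is the reading of treatment failures. Section 3.1 takes substances associated with failure to reach SVR forward to laboratory work when poor adherence does not account for the failure. If the cap series were the only evidence used there, missed Zepatier would go unseen.

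**Working it through.** **Reference figure.** The protocol gives no adherence rate, so there is nothing on this point to reproduce. Its one computed figure, 42 per group in section 9.1, concerns SVR12. With 95% in both arms, a 14-point margin, one-sided 5% and 90% power: (1.645 + 1.282)² × 2 × 0.95 × 0.05 / 0.14² = 41.5, which rounds up to 42. It reproduces and does not depend on Z_t.

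**Tracing the source for genotype 3.**

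| Arm and drug | Record described | Electronic? | Daily? |
|---|---|---|---|
| Fortnightly arms, Sovaldi | Cap on bottle (3.1, 5.5.2, 6.1.4) | Yes | Yes |
| Fortnightly arms, Zepatier | Count of leftover tablets (3.1, Table 2) | No | No, 14-day total |
| DOT, both drugs | Daily log (3.1, 5.5.2) | Not described as such | Yes |

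Only the first row can supply an electronically compiled dosing history. A two-week count gives a total without dates, so it cannot be converted into a daily indicator.

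**Size of the error from this source.** Let s be the share of days with a bottle opening and m the share of those days on which Zepatier was missed. Treat an opening as one Sovaldi tablet taken.

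- Z_t averages s.
- Days with both drugs taken average s(1 − m).
- The overstatement is s − s(1 − m) = s × m.

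Both s and m are assumed. Genotype 3 treatment lasts 8 weeks, or 56 days (section 6.2).

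| s | m | Z_t reports | Both drugs taken | Overstatement | Days of 56 |
|---|---|---|---|---|---|
| 0.80 | 0.05 | 80% | 76.0% | 4.0 points | 2.2 |
| 0.80 | 0.10 | 80% | 72.0% | 8.0 points | 4.5 |
| 0.80 | 0.20 | 80% | 64.0% | 16.0 points | 9.0 |
| 0.95 | 0.05 | 95% | 90.25% | 4.75 points | 2.7 |
| 0.95 | 0.10 | 95% | 85.5% | 9.5 points | 5.3 |
| 0.95 | 0.20 | 95% | 76.0% | 19.0 points | 10.6 |

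At m = 0 the overstatement is 0 for any s.

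**One hypothetical record.** The bottle is opened on all 56 days and 14 Zepatier tablets come back over the course. Z_t gives 56/56 = 100%. At most (56 − 14)/56 = 42/56 = 75% of days can have included both drugs. The trial's own tablet count would contradict its daily variable.

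**The case against.** The strongest reply is that section 9.2.3(c) defines Z_t correctly and names neither the cap nor Sovaldi. Combining two drugs into one indicator is a derivation rule, and the protocol promises an SAP. Zepatier intake is also measured, and section 9.2.2 lists pill counts beside cap data. Part of this stands: reading the electronic history as the cap record is an inference, and overall adherence rates need not rest on the cap alone. But the cap is the only electronic dosing record described, the protocol itself fixes the source of Z_t, and the counts listed in 9.2.2 are not brought into it. This is a stated rule that yields the wrong quantity, not a detail left for later.

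Several stronger readings are tempting and are not supported:

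- **That Z_t overstates adherence on balance.** A cap records openings, not ingestion. Someone who removes several tablets at one opening scores 0 on days when both drugs were taken. Only the component s × m has a known direction.
- **That the comparison with DOT is shown to favour the fortnightly arms.** Section 5.5.2 supplies DOT participants with tablets for weekends and closed days, so not every DOT dose is observed. If sites close on both weekend days (an assumption), that is 8 × 2 = 16 of 56 days. DOT has a log rather than a cap, so Z_t as written has no source there, and 9.2.3(c) names pathways that do not match this trial's arms.
- **That failures will be wrongly attributed to illicit drugs.** Section 3.1 does not say which adherence measure decides the matter.
- **That the food instructions separate the two doses.** In section 6.1.1 Sovaldi is "taken as one film-coated tablet once daily with food for 8 weeks", and Zepatier may be taken with or without food. These are compatible and show nothing about timing.

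**Conclusion.** The point holds for genotype 3 participants in the two fortnightly arms: Z_t generated as section 9.2.3(c) directs is a series of Sovaldi bottle openings and cannot reveal a missed Zepatier tablet. The overstatement from this source is s × m, 4.75 to 19 points at s = 0.95 and m = 5% to 20%. Those rates are assumptions, and the error vanishes if the tablets are always taken or missed together.

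It concerns one derivation of a secondary outcome in a subset of participants. SVR12 and the sample size are untouched. It is still worth correcting before the SAP is finalised, because it governs what may be claimed about regimen adherence and how failures to reach SVR are read. That Z_t also has no stated electronic source for DOT or for genotype 1 participants is a related gap that this correction does not close.

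**What to change.** In section 9.2.3(c), and in the SAP:

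1. Label the cap-based Z_t for genotype 3 as daily Sovaldi bottle opening, not regimen adherence.
2. Report the fortnightly Zepatier tablet count beside it.
3. Do not present the cap series alone as regimen adherence in any comparison with DOT.
4. Require both the cap record and the Zepatier count to be considered before a failure to reach SVR is classed as not accounted for by poor adherence (section 3.1).

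A combined fortnightly measure, the lower of opening days and Zepatier tablets taken divided by 14 doses due, could serve as a sensitivity analysis with its limits stated. It overstates adherence when the tablets are missed on different days: two Sovaldi misses and two Zepatier misses on four separate days give 12/14 = 86% against a true 10/14 = 71%. It understates adherence when several tablets leave the bottle at one opening: all doses taken with 10 openings gives 10/14 = 71% against a true 100%.

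The cost is wording only, since both records are already planned. The small downside is two adherence measures for genotype 3 instead of one, with the Zepatier measure not daily.

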## **9 STATISTICS AND DATA ANALYSIS**

### **9.1 SAMPLE SIZE CALCULATION**

Statistical analysis will be conducted in compliance with TASC SOPS.

We propose to conduct this project as a randomised trial to show that DAA therapy in very active PWIDs administered fortnightly with or without adherence intervention is non-inferior to DOT. We will compare pathways sequentially comparing DOT vs fortnightly delivery and then DOT versus fortnightly pickup with adherence intervention. Fortnightly pick up will be more cost effective than the other two options so long as adherence and efficacy matches that of the DOT and fortnightly plus adherence intervention. If we assume a 95% SVR rate (based on published studies) in the DOT arm of the trial in this population and a non-inferiority limit of 14% (which would be likely to maintain cost-effectiveness) then at a 5% significance level and 90% power

we would need a sample size of 42 in each group 126 in total. To allow for drop-outs we will aim to recruit 135 individuals, 45 per group.

A Statistical Analysis Plan (SAP) will be prepared for analysis of primary and secondary outcomes and will include a plan for handling missing data

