### 9.2.2 Secondary Outcomes

- Compare adherence to therapy rates of subjects randomised to either DOT, fortnightly therapy or fortnightly therapy with psychological adherence intervention - treatment of HCV. Adherence rates will be obtained from the daily log data in the DOT group, and from pill counting and MEMs caps data in the two fortnightly therapy groups.
- Assess reinfection rates in the PWID population and treated using all oral DAA regimes. The data for reinfection rates will be generated from the annual follow up and retesting for chronic HCV infection of all participants treated. This will be from routine clinical follow data and consent will be sought to access this. The analysis is simple, requiring only simple descriptive statistics.
- Assess viral resistance patterns in participants who do not achieve SVR. These data will be obtained by analysing samples for resistance associated variants (RAVs) using standard clinical laboratory assays.
- Assess the types of illicit drugs taken by trial participants and identify any interaction with the DAAs and possible effect on adherence. This data will be generated by the adverse event reporting mechanism within the trial. The particular interest will be around interactions of the trial medication with drugs of misuse. Concomitant drug use during the trial will be recorded in the CRF at baseline and end of treatment and supported by urine toxicology from a urine sample that will be collected during treatment. Data will be recorded in the CRF.

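### The either/or rule for adherence raises the false-positive rate to about 7–10% for one contrast if each term is tested at 5%, and the terms it tests need not measure overall adherence

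*Protocol*

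**What the plan says.** Protocol section 9.2.3, item c, defines a daily yes/no adherence variable for each patient and models it by "logistic regression where dependence among observations from a given patient over time is taken into account". It then states the purpose and the decision rule: "The effect of pathway and contingency management on overall adherence will be tested using the above-described model", and this is done "by testing if either the group coefficient or the interaction between the group and time are significantly different from zero". The item gives no significance level, no adjustment for two tests, no joint test and no time origin.

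The number of groups is not consistent. Item c speaks of one group coefficient and of a comparison "between the conventional pathway and the pharmacy led pathway". Section 9.2.2 sets a three-arm aim: "Compare adherence to therapy rates of subjects randomised to either DOT, fortnightly therapy or fortnightly therapy with psychological adherence intervention". The only significance level near this analysis is in section 9.1, where it serves the SVR sample size: "then at a 5% significance level and 90% power".

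Section 6.4 describes adherence as a secondary outcome.

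**The concern.** There are two faults, and they are separate.

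- **Error rate.** If a significant result on either of two terms counts as an effect, the chance of at least one false positive exceeds the level of each test. More arms tested coefficient by coefficient raise it further.
- **Target.** Once a group-by-time term is in the model, the group coefficient is the difference between groups at the time point coded zero, and the interaction is a difference in slope. Two adherence curves that cross, with the same average over the course, can give a significant interaction. The rule would call that an effect on overall adherence. A multiplicity adjustment does not cure this.

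Section 1.2 expects the comparison to show which pathway has the best compliance. Section 9.1 makes the cost-effectiveness of fortnightly pick-up conditional on its adherence matching the other arms. A rule that declares differences too readily, or mislabels them, bears on both statements.

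**Working it through.** **The plan's own figure.** The protocol states no error rate for the adherence test. Its only related figure is 42 per group in section 9.1, from 95% SVR (taken in both arms), a margin of 14 points and 90% power:

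n = (1.645 + 1.282)² × 2 × 0.95 × 0.05 / 0.14² = 8.57 × 0.095 / 0.0196 ≈ 41.5, so 42.

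This reproduces with a one-sided 5% level; one-sided 2.5% gives 51. That 5% therefore belongs to the non-inferiority calculation and does not settle the level for adherence. I assume 5% two-sided per test below.

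**One contrast, two tests.** If the two estimates are uncorrelated (time centred):

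1 − 0.95² = 0.0975.

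If time runs from zero over evenly spaced days, with independent errors, the correlation of the two estimates is −mean(t)/√mean(t²) = −(1/2)/√(1/3) = −0.866. The overlap lowers the rate to 7.3%.

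**Other readings.** The table gives the probability of at least one significant result under no arm effect. It comes from 1,000,000 draws of correlated normal test statistics with three equal arms; ρ is the correlation between the group and interaction estimates.

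| Reading of the rule | ρ = 0 | ρ = −0.5 | ρ = −0.866 |
|---|---|---|---|
| One contrast: group term or interaction | 9.7% | 9.1% | 7.3% |
| Three arms: one 2-df group test or one 2-df interaction test | 9.8% | 9.2% | 7.4% |
| Both fortnightly arms against DOT: any of four coefficients | 17.3% | 16.1% | 13.1% |
| All three pairs: any of six coefficients | 22.9% | 21.3% | 17.3% |

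Four independent tests would give 1 − 0.95⁴ = 18.5%. The 17.3% is lower because both contrasts share the DOT arm.

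**Check on binary data.** Null trials were simulated with 45 patients per arm, 56 daily values, random patient effects and a logistic fit with cluster-robust variance (six scenarios, 1,000 trials each). Rejection rates were:

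- one contrast: 9.3–12.4%;
- three arms, term by term: 9.6–12.6%;
- four coefficients: 16.9–20.5%;
- one joint 4-df test on the same data: 6.6–7.7%.

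The joint test's excess over 5% is small-sample inflation of the robust variance, so part of the excess in the other rows has the same cause. With time counted from the start, the average correlation was −0.43 to −0.54, which corresponds to about 9% for one contrast in the table.

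**Sensitivity to the assumed level.** At 2.5% per test, the one-contrast rate is at most about 1 − 0.975² = 4.9%. The excess exists only if each term is tested at the full level.

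**The case against.** Four objections deserve an answer.

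- **The 13–17% figure.** A reader might infer that this is the error rate of the plan. The text does not fix it. Item c names one group coefficient and two pathways, which gives 7–10%; three arms tested term by term give the same. The higher range needs four separate coefficients with any one counted as positive. This objection stands.
- **Neither term measures overall adherence.** A reader might take this to hold whatever the time coding. It does not: with centred time the group coefficient is the mid-course difference in log-odds, close to overall adherence. The top of each error range also belongs to centred time, so the highest error rate and the day-0 criticism do not apply together at full strength. This also stands. What remains is that the protocol does not state the coding, so the meaning of the test is open.
- **A joint test may have been meant, or the SAP may settle it.** A difference in either term is indeed the alternative hypothesis of a joint test, and level and coding are ordinary SAP content. But the wording asks whether either term is significant, which reads as two tests. It is a stated rule rather than an omission: an SAP that follows it literally inherits the fault.
- **The data are not as simulated.** Sections 3.1, 5.5.2 and 6.1.4 provide electronic caps only on Sovaldi bottles, hence only for genotype 3 participants in the fortnightly arms. Genotype 1 pick-up participants have fortnightly tablet counts and are treated for 12 weeks rather than 8. Daily series on 45 patients per arm will not exist. This stands: it limits both the simulation and any remedy built on daily data.

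Nor does the protocol rank adherence above the other secondary outcomes, or attach a confirmatory claim to this test.

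**Conclusion.** The concern holds in a limited form. As worded, the either/or rule has a false-positive rate of about 7–10% for one contrast or for term-by-term tests across three arms. It is about 13–17% only if both fortnightly arms are tested against DOT coefficient by coefficient. These figures assume 5% two-sided per test, no adjustment, and a correlation between the terms from 0 to −0.866.

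The interaction never measures overall adherence. The group coefficient does not if time starts at the beginning of treatment, and comes close if time is centred. The sample size and the primary SVR conclusion are untouched. This is a wording fault in a secondary analysis, worth correcting because the correction is cheap.

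**What to change.** Replace the either/or clause in section 9.2.3, item c, and carry the change into the SAP:

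1. Prespecify one test at 5%. This is either a joint test of all group and group-by-time terms (2 df for a pair, 4 df for three arms) or a single named contrast of average adherence.
2. Whichever test is chosen, report the between-arm difference in the average proportion of doses or days adherent over the course, with a 95% CI. A joint test alone shows that the curves differ somewhere; it does not isolate overall adherence.
3. State the time origin, and name the three randomised arms in place of the two pathways.
4. Apply the daily model only where daily records exist: the DOT log, and the electronic caps for genotype 3 pick-up participants. Use tablet counts for genotype 1 pick-up participants. A like-for-like daily comparison of arms is then confined to genotype 3.

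The cost is a few sentences of wording and slightly fewer nominally significant adherence results. No data collection changes.

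### About 7 to 15 expected SVR failures are too few for the exploratory multiple logistic regression of SVR if arm, genotype and all listed covariates enter together

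*Protocol*

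**What the plan says.** Protocol section 9.2.3 ends with an exploratory analysis: "Multiple logistic regression modelling will explore the patient and pathway characteristics that are associated with the secondary outcomes and primary outcome". The candidates follow: "Patient outcomes considered will be age, gender, deprivation, employment, comorbidity, and the psycho-social variables assessed". The text sets no limit on the number of terms, gives no rule for choosing them and names no small-sample method. It does not say how many psycho-social variables there are.

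The expected number of failures follows from section 9.1, which sizes the trial on "If we assume a 95% SVR rate (based on published studies) in the DOT arm", with "a non-inferiority limit of 14% (which would be likely to maintain cost-effectiveness" as the margin, "at a 5% significance level and 90% power". It concludes "we would need a sample size of 42 in each group 126 in total", and then: "To allow for drop-outs we will aim to recruit 135 individuals, 45 per group".

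Two other rules bear on the count. Section 9.2.3 uses all randomised participants as the denominator for SVR and counts drop-outs and losses to follow-up as failures. Section 9.3 repeats that incomplete primary data count as failure.

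**The concern.** In a logistic model the information comes mainly from the rarer outcome. SVR is expected in about 95% of participants, so the rarer outcome is failure, and 135 participants yield only a handful. A model with more parameters than failures, or nearly as many, tends to show separation: some combination of covariates splits failures from successes, and a maximum-likelihood odds ratio runs to infinity. Where the fit does converge, log odds ratios are biased away from zero and the intervals are very wide.

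At stake is what the trial says about which patients and which delivery pathways fail treatment. Readers planning services will look for that. Apparent predictors from such a fit could be artefacts of sparse data.

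**Working it through.** **Step 1: reproduce the plan's own figure.** With both compared arms at 95%, a margin of 0.14, one-sided 5% and 90% power:

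n per group = 2 × 0.95 × 0.05 × (1.645 + 1.282)² / 0.14² = 0.095 × 8.567 / 0.0196 = 41.5, so 42.

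This matches section 9.1. One-sided 2.5% would give 51. The match shows that 95% is also the planning value for the comparator arm.

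**Step 2: expected SVR failures.**
- If 95% is the rate for the endpoint as defined, with drop-outs already inside it: 135 × 0.05 = 6.75.
- If the drop-out allowance (135 − 126 = 9) is added as failures: 9 + 126 × 0.05 = 9 + 6.3 = 15.3, which is 15.3 / 135 = 11.3%.

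The protocol does not say which reading applies, so the range is about 7 to 15.

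**Step 3: parameters if everything enters together.**
- Arm 2, genotype 1, five named covariates at one parameter each, one psycho-social variable: 2 + 1 + 5 + 1 = 9.
- With deprivation in quintiles (4 parameters instead of 1) and two psycho-social scores: 9 + 3 + 1 = 13.

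**Step 4: failures per parameter.**
- 9 parameters: 6.75 / 9 = 0.75 and 15.3 / 9 = 1.7.
- 13 parameters: 6.75 / 13 = 0.52 and 15.3 / 13 = 1.18.

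**Step 5: simulated consequence.** Each scenario had 1,000 trials of 135 with no true effects and the same failure risk in every arm. Separation was detected by linear programming. These inputs are assumptions and do not come from the protocol: genotype split 50:50, 30% female, 40% with comorbidity, continuous covariates standard normal, and one binary covariate (standing for employment) at the prevalence shown. The CI columns give the typical ratio of upper to lower 95% limit for an odds ratio in fits that did not separate.

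| Terms | Prevalence | Infinite OR, 6.75 failures | Infinite OR, 15.3 failures | CI ratio, 6.75 | CI ratio, 15.3 |
|---|---|---|---|---|---|
| 9 | 10% | 67% | 23% | 27 | 11 |
| 9 | 30% | 42% | 3% | 30 | 11 |
| 9 | 50% | 37% | not run | 29 | not run |
| 13 | 10% | 88% | 37% | 53 | 18 |
| 13 | 30% | 82% | 22% | 37 | 15 |
| 13 | 50% | 80% | not run | 34 | not run |

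With arm and genotype alone (3 terms), separation occurs in 27% of trials at 6.75 failures and 1% at 15.3. At the low count, then, fewer terms alone do not remove the problem.

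Although every true odds ratio is 1, the largest absolute log odds ratio in a typical converged 9-term fit is about 1.46 to 1.48 at 6.75 failures and 1.12 to 1.15 at 15.3. These correspond to odds ratios of about 4.3 to 4.4 and about 3.1, or their inverses.

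**Step 6: more failures than planned.** With 9 terms and the 10% prevalence, a 15% failure rate (20.25 failures, 2.25 per parameter) gives separation in 14% of trials and a CI ratio of 8.3. A 20% rate (27 failures, 3.0 per parameter) gives 8% and 6.6.

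**The case against.** The strongest reply has four parts.

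- **The count of 7 leaves out drop-outs.** Under the protocol's failure rule and its allowance of nine, about 15 can be expected. This stands as the upper end of the range. At 15 failures only a minority of fits separate, but 1.7 failures per parameter is still too few for usable estimates.
- **No joint model is specified.** Section 9.2.3 speaks of exploring characteristics and of variables considered. Adjustment for therapy and genotype is stated for the primary model. This stands, so the finding is conditional on the covariates entering together. Multiple regression on patient and pathway characteristics does naturally mean several terms at once, and nothing in the text restricts how many.
- **Maximum likelihood is not named.** True, and a Firth fit is also logistic regression. But ordinary maximum likelihood is the default when nothing else is said.
- **The SAP may settle it.** The SAP is promised before data lock and is not shown, so it may limit the terms or choose another estimator. The point is therefore not that detail is missing. The method, the outcome and the candidate list named in the protocol fit poorly with the number of failures the protocol implies.

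A reader might infer that most fits would give infinite odds ratios. The documents do not support that: it holds only near 7 failures with a rare covariate or multi-level coding. A reader might also infer that the primary result is at risk. The covariate list is not part of the primary model, and the 14-point margin is on the scale of proportions.

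**Conclusion.** The point holds in a limited, conditional form. The protocol's assumptions imply about 7 to 15 SVR failures. If arm, genotype and the listed covariates enter one model of about 9 parameters, that is 0.75 to 1.7 failures per parameter. Ordinary maximum likelihood would then give an infinite odds ratio in roughly 40% to 65% of trials at the low count and roughly 3% to 25% at the high count. In the 9-term fits that converge, the upper 95% limit is typically about 27 to 30 times the lower at 7 failures and about 11 times at 15.

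The failures per parameter depend on carrying the 95% rate to all three arms and on the parameter count. The separation percentages depend further on assumed covariate distributions and coding; the prevalence of a single covariate moves the 9-term result at 7 failures from 37% to 67%. Small-sample bias in the converged fits is a general property of maximum likelihood and was not estimated separately here.

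The analysis is exploratory, it also covers secondary outcomes that may have more events, and the primary non-inferiority comparison is not affected. This is a cheap improvement, not a flaw in the main design.

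**What to change.** State in the SAP, and in section 9.2.3 if the protocol is amended, that for SVR:

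- the exploratory models are fitted by Firth penalised (or exact) logistic regression;
- the number of terms is limited to what the observed failures support, for example arm and genotype plus one patient covariate at a time;
- odds ratios are reported with 95% CIs and labelled exploratory;
- the full multivariable model is kept for outcomes with enough events.

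The cost is wording only, with no new data or participants. The downside is that SVR will have no mutually adjusted covariate estimates, which 7 to 15 failures could not support in any case.
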